10.3 Subject's Identification and Confidentiality

A unique number will be assigned to each subject following information consent has been obtained. This number will be used as subject's identification in the study, as well as in the clinical study database. All data collected from study subjects will be recorded in appropriate charts. Only the Investigator will be able to link the test's data for a subject by means of an identification list will be located at the site. For each subject, clinical data will be available for verification purposes by the monitor, audits and regulatory inspections, but subject's confidentiality will be strictly kept.

Data protection and confidentiality will be kept during data entry, processing, submission and storage. Subjects will be informed about it and they will be requested to provide their consent for data management according to the national regulations.

The Ministry of Health, Ethics and Investigation Committee and the Investigational Committee will be the only authorized bodies for reviewing study documentation, (which includes participant subject's identity data) and documents considered confidential by clinical unit at the PPD [REDACTED] and by the analytical unit from Merck.

10.4 Medical Insurance and Subjects' Compensation

Subjects will sign a consent which states that they will receive an economical compensation for their participation in the study. The Sponsor will pay treatment (or compensation, if applicable) resulting from injuries or diseases caused by their participation in the study until their resolution as per the clinical criteria. The Sponsor will not pay injuries caused by subject's negligence, irresponsible behavior or medical reasons not related to the study.

10.5 Ethics and Investigation Committee and Investigational Committee

Before study start-up, approval from the Ethics and Investigation Committee and from the Investigational Committee will be obtained. They should provide a list of the members who compose it, as per request from the Study Sponsor or Principal Investigator. If necessary due to amendments to the clinical protocol, case report form or informed consent form, a new approval should be got from both Committees.

10.6 Health Authorities

The clinical protocol as well as the appropriate documents will be submitted to the health authorities, according to the local and national applicable regulations.

11 Study Management

11.1 Case Report Form

Case Report Forms will be completed by authorized medical staff according to the standard operating procedure, code: PPD [REDACTED] Good documentation practices, with legible letter and without amendments.

Paper CRF will be fully and legibly completed, using blue ink appropriate for use in official documents. Necessary amendments or corrections should be made, dated and confirmed by the Investigator or designated personnel. Whenever corrections are made to data, original entries should remain legible, and should not be deleted or corrected. Investigator or designated personnel should state reasons of corrections of relevant data. For any missing information or comments, blanks should be voided to avoid unnecessary follow-up queries. CRF's are essential documents which should be available for regulatory inspections and submissions.

11.2 Source Document and Subject's Medical Chart

The Principal Investigator should keep a paper or electronic file (medical file, and original medical records) for each subject in the study. It should be possible to identify each subject by means of this file. This file will contain the following subject's demographic and medical information and should be as complete as possible.

- Subject's complete name, date of birth, sex, height and weight.
- Medical history.
- Previous concomitant therapies (including changes during the study).
- Study identification; i.e., subject's number.
- Study recruitment dates (informed consent) and visits to the site.
- Any medical exam and pre-defined clinical findings in this clinical protocol.
- All adverse events.
- Date when the subject withdraw his/her consent, including any reason for withdrawal.

All documents which contain source data should be shown, including but not limited to, electrocardiograms and laboratory tests results. These documents should have subject's number and date of procedure. If possible, this information should be printed by the equipment used to perform the assessment or measurement. As necessary, medical assessment should be conducted; all assessments should be documented, signed and dated by the Principal Investigator.

11.3 Site's File and Master File

At the beginning of the study, the Principal Investigator will receive a master file for the site which contains all necessary study documents to be completed throughout the study and which will be updated as necessary. Master file should be available for Monitor's review, Sponsor's audits and Health Authorities' inspection during and following study. It should be securely filed for at least 15 year (or more, according to the local needs or otherwise stated by the Sponsor) following study completion. Documents to be filed include the subject's identification list and the signed informed consent by the subject. In the even the master file cannot be kept at the site anymore, Principal Investigator should inform the Sponsor/designated person.

All subjects' source documents (medical charts) should be stored at the site as long as possible, as allowed by applicable guidelines and/or according to the ICH GCP guidelines, whatever is longer. In any case, the Principal Investigator should ensure that no destruction of medical charts is done without written approval form the Sponsor.

11.4 Quality Management

Quality assurance is performed by means of follow-up to the standard operating procedures, codes: PPD [REDACTED] Elaboration of quality assurance report for clinical trials; PPD [REDACTED] First stage of quality control and quality assurance review during clinical studies conduct; PPD [REDACTED] Second stage of quality control and quality assurance review during clinical studies conduct; and PPD [REDACTED] Third stage of quality assurance review during clinical studies conduct.

Quality Management follows up the conduct of the study by means of quality control monitoring for the review of compliance with the clinical protocol, internal standard operating procedures, and applicable guidelines according to the GCP (ICH E6R1). Discrepancies and areas of improvement identified are followed up according to the standard operating procedure, code: PPD [REDACTED], Discrepancies identification and follow-up, potential causes of discrepancies and continuing improvement. All information collected is analyzed for the preparation and issue of the Quality Assurance report.

11.5 Changes to the Protocol

Protocol amendments can be issued by the Principal Investigator and agreed with the Sponsor or vice-versa. Substantial changes have to approve by the Ethics and Investigation Committee and by the Investigational Committee. Administrative changes (non substantial changes) which do not affect the study will be agreed with and approved by the Sponsor, the analytical unit and by the Principal Investigator. They will also be notified to the Ethics and Investigation Committee and to the Investigational Committee.

11.6 Study Report and Publication Policy

11.6.1 Clinical Study Report

After study completion, the Principal Investigator with Sponsor's advice will prepare the clinical study report according to the Mexican Official Standard which states tests and procedures to show that drug is interchangeable. Requirements which authorized third parties should fulfill for interchangeability tests. Requirements for performing biocomparability studies. Requirements which authorized third parties, investigational sites and hospitals conducting biocomparability tests should fulfill (NOM-177-SSA1-2013) and applicable guidelines.

11.6.2 Publication

All data and results, and all intellectual property rights for data and outcomes from the study will be property of Merck KGaA, which may use data for different purposes such as, submission to government health authorities or submission to other investigators.

The Investigator, although is free to use data derived from the study for scientific purposes, but has to discuss any publication with Merck in advance and obtain Sponsor's written consent for the pursued publication.

The Sponsor acknowledges the Investigator's right to publish outcome once the study is completed. Anyway, the Investigator should submit a draft of the paper or summary to be published to Merck 30 days before submitting the final version for publication.

It will be reviewed soon and approval will not be unnecessarily delayed. In case of controversies between the Sponsor and the Investigators, publication content will be discussed in order to find a satisfactory solution for both parties.

12 Deviations to the Protocol

Deviations to the research protocol which occur during study conduct should be documented. The Principal Investigator, the Study Sponsor have to be informed immediately. Ethics and Investigation Committed and to the Investigational Committee.

When a protocol deviation occurs during the clinical stage, the Principal Investigator should assess it and consider if study subject's continuation may affect protocol's outcome. Sponsor will be informed and jointly they will make a decision about subject's continuation in the study.

13 **References**

- ✚ American Diabetes Association. Standards of Medical Care in Diabetes 2014. *Diabetes Care* 2014;37(Supp.1).
- ✚ Chow, S.C. and Wang, H. (2001). On sample size calculation in bioequivalence trials. *Journal of Pharmacokinetics and Pharmacodynamics*, 28, 155-169.
- ✚ DIAMICRON MR: gliclazida. Responsável Técnico: Patrícia Kasesky de Avellar. Rio de Janeiro: Laboratórios Servier do Brasil Ltda. [2013]. Bula de medicamento.
- ✚ Drugs classification according to risks during pregnancy and breastfeeding (FDA) obtained at <http://www.drugs.com/pro/glucophage.html>.

Appendix 2: Diet

Diet to be given to subjects following dose in each of the periods will be the same in quantity and content to that provided during the previous period.

Energetic Distribution			
Group	%	g	Kcal
Carbohydrates	55	275	1100
Proteins	15	75	300
Lipids	30	67	600
Total Kcal	----	----	2000

Appendix 3: Drugs classification according to risks during pregnancy and breastfeeding (FDA)

A	Without apparent risks	Controlled studies in women do not show risk for the fetus during the first quarter; therefore, likelihood of fetal damage seems to be remote. They can be used.
B	Without apparent risks	Studies in animals do not show any risk for the fetus and there are no controlled studies in humans. Studies in animals do show adverse effects for the fetus; however, well controlled studies in pregnant women have not shown fetal risk. Probably safe
C	Undetectable risk	Studies in animals have shown that the drug has teratogenic or embryonic effects. There are no controlled studies or there are no studies available in animals or women. Avoid them if there is any other option.
D	Proven risk	There is positive evidence about fetal risk in humans but, in some cases (for instance, life-threatening situations or severe illnesses where more secure drugs cannot be used or which they turn to be not effective), benefits can make the drug acceptable in spite of the risks. Avoid them if there is any other option.
X	Contraindicated drugs	Studies in animals and humans have shown fetal abnormalities, or there is evidence of fetal risk based on the experience in human beings; or both situations apply and risk clearly overcomes possible benefit. Contraindicated drugs

SASS	Sino-American Shanghai Squibb Pharmaceuticals Ltd
SAP	Statistical Analysis Plan
SBP	Systolic Blood Pressure
SD	Standard Deviation
SDTM	Study Data Tabulation Model
SEM	Standard Error of the Mean
SOC	System Organ Class
t _{1/2}	Apparent terminal half-life
T2DM	Type 2 Diabetes Mellitus
TEAE	Treatment-Emergent Adverse Event
TLF	Tables, Listings, and Figures

t_{last}	The last sampling time at which the concentration is at or above the lower limit of quantification
t_{max}	The time to reach the maximum observed concentration
TP	Treponema Pallidum
$V_{z/f}$	Apparent volume of distribution during the terminal phase following extravascular administration
λ_z	Terminal elimination rate constant
WHO	World Health Organisation

4

Modification History

Unique Identifier for SAP Version	DATE OF SAP Version	Author	CHANGE DESCRIPTION from the previous version	LEVEL
	March 2019	PPD	New Document	1.0

5

Purpose of the Statistical Analysis Plan

The purpose of this SAP is to document technical and detailed specifications for the final analysis of data collected for protocol BD1412-62CEC EMR200763-003. Results of the analyses described in this SAP will be included in the Clinical Study Report (CSR). Additionally, the planned analyses identified in this SAP will be included in regulatory submissions or future manuscripts. Any post-hoc.

The SAP is based upon section 9 (Statistical and Pharmacokinetical Analysis) of the trial protocol and is prepared in compliance with ICH E9.

6

Summary of Clinical Trial Features

6.1

Primary Objectives and Endpoints

- To demonstrate bioequivalence of the fixed combination of Metformin tablets 1000 mg XR plus Gliclazide 30 mg MR compared to the co-administration of the individual tablets of Metformin 1000 mg XR and Gliclazide 30 mg MR, given as single dose to healthy volunteers in fasting state. Primary endpoints will be AUC_{0-t}, AUC_{0-∞} and C_{max} for Metformin and Gliclazide.
- To demonstrate the lack of an effect of Gliclazide on the PK of Metformin by comparing the Metformin PK following administration of the fixed combination tablet Metformin/Gliclazide and Metformin alone (AUC_{0-t}, AUC_{0-∞} and C_{max} of Metformin).
- To demonstrate the absence of an effect of Metformin on the PK of Gliclazide by comparing the Gliclazide PK following administration of the fixed combination tablet Metformin/Gliclazide and Gliclazide alone (AUC_{0-t}, AUC_{0-∞} and C_{max} of Gliclazide).

6.2

Secondary Objectives and Endpoints

- The secondary endpoints variable are volume of distribution K_e, half-life elimination, clearance, and median residence time all these parameters will be presented only for informative reasons for both medications.
- To compare the safety and tolerability of all the experimental treatments.

6.3

Overall Trial Design and Plan

This randomized, open-label, single dose, four-treatment, four period crossover design (4x4) trial with a 14-day wash-out period along 4 study stages will investigate the bioequivalence (primary endpoints are AUC_{0-t}, AUC_{0-∞} or C_{max} for Metformin and Gliclazide) of a Metformin/Gliclazide fixed combination tablet (1000 mg /30 mg MR) compared with the co-administration of the individual tablets (Metformin 1000 mg and Gliclazide 30 mg MR) and the drug-drug interaction between the Metformin/Gliclazide fixed combination and the administration of each single tablet, administered in fasted condition in 40 healthy volunteers. Secondarily, safety and tolerability will be also investigated in every case.

The subjects will be randomized to one of the 4 treatment sequences (see table below). Ten subjects will be randomized to each treatment sequence with a minimum proportion of 30% for each sex in each treatment sequence.

Sequence	Period 1	Wash-out period	Period 2	Wash-out period	Period 3	Wash-out period	Period 4
			Metformin + Gliclazide		Metformin		Gliclazide
1	Fixed combination		Gliclazide		Fixed combination		Metformin
2	Metformin + Gliclazide		Metformin		Gliclazide		Metformin + Gliclazide
3	Metformin		Fixed combination		Metformin + Gliclazide		Fixed combination
4	Gliclazide		Metformin				

7

Sample Size

The sample size estimation is based on the CV intrasubject variability of both drugs. Because the pharmacokinetic and drug-drug interaction, evaluates changes in the bioavailability, the propose is the use the same determination for both aims.

The sample size is determined by the primary endpoint with the greatest variability under fasting conditions, AUC_{0-t} of Metformin (CV=23%). Assuming a mean treatment ratio of 0.95, and aiming at a power of 90% for the individual test, alpha=0.05 one-sided, 32 evaluable subjects are sufficient to demonstrate bioequivalence in the first step. The same arguments can be applied to the second step: Test absence of an effect of Gliclazide on the PK of Metformin, whereas the power for the third test is close to 100% with 32 subjects, due to the low variability of Gliclazide PK. Therefore, the overall power is still greater than 80% with 32 evaluable subjects. Considering a drop-out rate of approximately 20%, 40 subjects should be randomized.

According to NOM-177-SSA1-2013, this sample determination was realized with Chow & Wang (2001) equation

$$n \geq [t_{(\alpha, 2n-2)} + t_{(\beta, 2n-2)}]^2 \cdot \left(\frac{CV_{intra}}{\ln 0.8 - \ln \theta} \right)^2$$

Where:

$t_{(\alpha, 2n-2)}$ and $t_{(\beta, 2n-2)}$ considered the error alfa and beta respectively

CV_{intra} : intra subject variability for crossover (or replicate crossover) study.

θ : 0.95: the target ratio in average BA between the two formulations expressed in percentage of the average reference

0.8: the least statistical power to detect (1-Power) differences between the Test and the Reference formulation (in this case the power expected is 90%)

8

Overview of Planned Analyses

Statistical analysis and analysis of PK parameters will be performed using Phoenix WinNonlin software Version 6.3 (PPD ██████████).

Descriptive statistical methods will be used to summarize demographic characteristics, pharmacokinetics parameters and adverse events. After the data base closing

Individual plasma concentration-time will be tabulated and plotted. Primary pharmacokinetics parameters, AUC and Cmax, will be tabulated and plotted by subject. Likewise, differences and odd ratios for test/reference will be tabulated for each subject for those parameters. Plasma concentration - time graphs will be made using arithmetic and semi-logarithmic scale. All de calculations will be determinated in concordance with NOM-177-SSA1-2013

The following sequential testing of a priori ordered hypotheses will be applied, as shown below. Bioequivalence test methodology will be used in all 3 steps:

1. Test bioequivalence of fixed combination and separate tablets
2. Test absence of an effect of Gliclazide on the PK of Metformin
3. Test absence of an effect of Metformin on the PK of Gliclazide

8.1

Interim Analysis

Bioequivalence in step1:

A mixed model will be applied to log-transformed Cmax, AUC0-t and AUC0-∞ (both analytes) with treatment, period and sequence as fixed effects, and subject (sequence) as a random effect. Based on the residual error term 90% confidence intervals will be computed for the estimated

differences Test – Reference, resulting in 90% confidence intervals for the Test/Reference ratios after back-transformation.

Drug-drug interaction in steps 2 and 3:

A mixed model will be applied to log-transformed Cmax, AUC0-t and AUC0- ∞ (one analyte) with treatment as fixed effect, and subject as a random effect. Based on the residual error term 90% confidence intervals will be computed for the estimated differences Test – Reference, resulting in 90% confidence intervals for the Test/Reference ratios after back-transformation.

1. Bioequivalence will be concluded, if all six 90% CIs for all six primary endpoints reside within the acceptance range [0.80 – 1.25]
2. Absence of an effect of Gliclazide on the PK of Metformin will be concluded, if all three 90% CIs for Metformin endpoints reside within the range [0.80 – 1.25]
3. Absence of an effect of Metformin on the PK of Gliclazide will be concluded, if all three 90% CIs for Gliclazide endpoints reside within the range [0.80 – 1.25]

Additionally, the primary endpoints will be descriptively analyzed and graphical displays (Box-whiskers-plots) will be prepared.

Statistical model in the variance analysis of mixed effects should be applied for log-transformed parameters Cmax, AUC0-t and AUC0- ∞ (one analyte) with TREATMENT as fixed effect and SUBJECT as randomized effect. Based on residual errors, confidence interval of 90 % will be built for estimated differences for test - reference, resulting in a confidence interval of 90 % for the test/reference ratio following transformation.

Using minimum mean squares for AUC and Cmax, two-side t test will be performed (Schuirmann's test) by constructing confidence intervals of 90 % for test/reference ratios. If and only if intervals are within interval (80, 125), bioequivalence will be proven for both drugs.

Bioequivalence is concluded if 6 confidence intervals for the analytes are included into the bioequivalence limits.

9 Changes to the Planned Analyses in the Clinical Trial Protocol

The statistical methods as described in the protocol were adopted.

There are no changes to the planned analyses.

10 Protocol Deviations and Analysis Sets

10.1 Definition of Protocol Deviations and Analysis Sets

All deviations should be justified with statistical or scientific data and any change to the original statistical plan should be documented, in the study master file and in the pharmacokinetics statistical report as well as in the final study report. Subjects' data will not be replaced. Any missing

data will be considered as non-existent data. Likewise, data cannot be removed from the statistical analysis, except in the following events.

▪ **Research Subjects with Pre-dose Concentrations in the Biological Matrix**

In the event pre-dose concentration is < 5 % of the C_{max} value for a research subject, subject's data can be included without any adjustment to measurement and pharmacokinetic calculations. When pre-dose value is > 5 % of the C_{max} , research subject should be removed from all study bioequivalence assessments.

▪ **Exclusion of data due to vomit or diarrhea.**

Data from research subjects who experience vomiting and diarrhea throughout the bioequivalence study for immediate release products can be removed from the statistical analysis if vomiting and diarrhea occur before 2 fold the median for t_{max} or 2 fold t_{max} value obtained from the research subject in a given period.

▪ **Research subject with very low plasma concentrations for study drugs.**

As established by NOM-177-SSA1-2013, research subjects in a cross designed who provide evaluable data for test drug and reference drug, or who do not have evaluable data in the single period of a parallel design, should not be either included in the statistical analysis.

It is considered that a research subject has very low concentrations, if the AUC is lower than 5 % of the geometric means for the reference drug's AUC (it should be calculated without including outliers). Exclusion of data due to this reason will only be accepted prior scientific rationale and review of the case by the COFEPRIS.

11 General Specifications for Statistical Analyses

Pharmacokinetic parameters (non-compartmental analysis) and statistical analysis for determining bioequivalence will be calculated using Phoenix WinNonlin 8.0 software.

The results of this trial will be reported using summary tables, figures, and data listings, as appropriate. All data will be summarized by treatment and/or scheduled time point, as appropriate.

12 Protocol Deviations

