8.9 Assessment of Study Drug Compliance

Throughout dosing period, dose, full intake and time will be checked and recorded in the appropriate forms, according to the standard operating procedure, code: PPD [REDACTED]. Preparation and administration of drugs in clinical trials of interchangeability and biocomparability; PPD [REDACTED]. Randomization in an interchangeability and biocomparability clinical study

A subject is compliant with the treatment only if he/she completes all study periods.

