9.9.3 PK Analysis Set

The PK Analysis Set will include all subjects who have completed the trial with adequate trial medication compliance, without any relevant protocol violations with respect to factors likely to affect the comparability of PK results, and with sufficient evaluable data to determine primary endpoints (AUC_{0-t}, AUC_{0-∞} and C_{max}) for both analytes. If subjects received concomitant medication for the treatment of an AE, their inclusion in the PK population needs to be discussed on a case-by-case basis.

All PK analyses will be based on this Analysis Set.

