9.9.4 Safety Analysis Set

All the deviations must be justified with statistical or scientific evidence and any change to the original statistical plan must be reported, in the master file of the study and in the statistical pharmacokinetic report and final report of the study

Subject data will not be replaced, any data missing will be considered as a non-existing data and likewise data cannot be eliminated from the statistical analysis, except in the following cases:

Research subjects with pre-dose plasma concentrations in the biological matrix.

If the pre-dose concentration is lower than 5% of the C_{max} value in a subject, the subject's data can be included without adjustment in all measurements and pharmacokinetic calculations. In the cases where the pre-dose value is greater than 5% of C_{max}, the research subject must be eliminated from all study evaluations.

Data elimination due to vomiting or diarrhea

Data from research subjects who experimented vomiting or diarrhea during the course of a clinical study for immediate release products can be eliminated from the statistical analysis if the vomiting or diarrhea occurred before 2 times the median of T_{max} or 2 times the value of T_{max} obtained in the research subject during a given period.

A research subject with very low plasma concentrations for study drugs

As established by the Mexican Official STANDARD NOM-177-SSA1-2013, also research subjects that in a crossover design do not provide assessable data, both from test drug and reference drug, should not be included in the statistical analysis.

A research subject is considered to have very low concentrations if the AUC is lower than 5% of the geometrical mean of the reference medication AUC (must be calculated without inclusion of data of the research subject with atypical values).

Data exclusion due to this reason will only be accepted under scientific justification and previous review of the case by the Federal Commission for the Protection against Sanitary Risks (Comisión Federal para la Protección contra Riesgos Sanitarios, COFEPRIS).

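### SAP 10.1 and 12.2 reverse the evaluability exclusion, and the pre-dose and vomiting removal rules do not fit this trial or agree with the protocol (minor, wrong as written)

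*SAP*

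**What the plan says.** **Evaluability.** On who enters the analysis, protocol 9.9.4 states that "research subjects that in a crossover design do not provide assessable data, both from test drug and reference drug, should not be included". SAP 10.1 and 12.2 restate this for "research subjects in a cross designed who provide evaluable data for test drug and reference drug", again with the consequence that they are not included. SAP 9 states: "There are no changes to the planned analyses".

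**Analysis set.** Protocol 9.9.3 defines the PK Analysis Set as "all subjects who have completed the trial with adequate trial medication compliance", without relevant violations and with enough data on both analytes, and adds: "All PK analyses will be based on this Analysis Set". Protocol 8.9 adds: "A subject is compliant with the treatment only if he/she completes all study periods". SAP 10.1 has analysis sets in its heading but contains only removal rules.

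**Closed list of removals.** Protocol 9.9.4: "data cannot be eliminated from the statistical analysis, except in the following cases". SAP 10.1: "data cannot be removed from the statistical analysis, except in the following events". Both then list three cases: pre-dose concentrations, vomiting/diarrhoea, and very low concentrations. The evaluability sentence sits under the third.

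**Pre-dose value above 5% of Cmax.** Protocol 9.9.4 removes the subject from every evaluation in the study, SAP 10.1 from the bioequivalence assessments, and SAP 12.2 from a food-effect study.

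**Vomiting.** Protocol 7.3.4 item 9 withdraws a subject who vomits within the dosing interval and removes that subject from the analysis. The listed exception (protocol 9.9.4, SAP 10.1 and 12.2) permits removal, does not require it, uses a window of twice tmax, and is confined to immediate-release products. The protocol joins vomiting and diarrhoea with 'or', the SAP with 'and'.

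**The concern.** These rules decide who enters the 12 confidence intervals on which the three conclusions rest: six for step 1 and three each for steps 2 and 3. An analyst should be able to apply them as written and reach one set of subjects.

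Here the evaluability rule, applied literally, excludes the subjects the analysis needs. SAP 12.2's pre-dose rule points to an analysis the trial does not contain. The vomiting exception describes a product type not under study, while another protocol section calls for removal in an overlapping situation. With SAP 9 declaring no changes, the reader is not told which text governs.

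**Working it through.** **1. Evaluability, side by side.** Protocol 9.9.4: subjects who do *not* provide data on test and reference are out. SAP 10.1 and 12.2: crossover subjects who *do* provide them are out. The SAP sentence goes on to a parallel-design clause that keeps its negation, and its subheading concerns very low concentrations. Both point to an omission, not a new rule. Taken literally, no subject with evaluable test and reference data remains. With the negation restored, all of them remain.

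**2. Pre-dose rule against the design.** All four treatments are given fasting (protocol 7.1, SAP 6.3), so there is no food-effect comparison and the SAP 12.2 sentence removes nobody. SAP 10.1 does remove such subjects, but names only bioequivalence assessments. SAP 8 uses bioequivalence methodology in all three steps, which supports a wide reading without stating it.

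How often could the rule be triggered? The wash-out is 14 days = 336 h (protocol 9.2.2).
- Gliclazide half-life 12–20 h (protocol 3.2.5): 336/20 = 16.8 to 336/12 = 28 half-lives.
- Metformin half-life about 6.5 h (protocol 3.1.5): 336/6.5 ≈ 52 half-lives.
- Residual at 16.8 half-lives: 2^(−16.8) ≈ 0.000009, about 0.001%, against the 5% threshold.

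On the documents' own figures, carry-over of that size is remote.

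**3. Vomiting and diarrhoea.** The study products are XR/MR, so the listed exception, read as written, never applies.
- *Vomiting:* 7.3.4 item 9 calls for removal, but the closed list in 9.9.4 has no case that allows it for these products. This conflict lies within the protocol, and the SAP carries it on.
- *Diarrhoea:* 7.3.4 item 9 does not mention it, so the inapplicable exception is the only rule that does. The SAP's 'and' would also require both symptoms.

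Protocol sections 3.1.8 and 4 list gastrointestinal disorders, including vomiting and diarrhoea, as very common (at least 1 in 10), and three of the four treatments contain metformin.

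**4. Sample size, reproduced.** Inputs (protocol 9.7, SAP 7): CV 23%, ratio 0.95, one-sided alpha 0.05, power 90%, df 2n − 2.
- σ = √ln(1 + 0.23²) = 0.2270
- ln 0.80 − ln 0.95 = −0.1719
- n ≥ (1.697 + 1.310)² × (0.2270/0.1719)² = 15.8, so 16 per sequence of a two-sequence design, 32 in total
- 32/(1 − 0.20) = 40 randomised
- Exact power of the two one-sided tests, limits 0.80–1.25, df n − 2, variance factor 2/32 = 0.0625: **0.904**

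(With 0.23 itself as σ, the formula gives 17 per sequence, 34 in total.) The stated figures hold and none of the wording changes touches them.

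**5. Dependence of that power on balance.** Suppose, for illustration, that all eight drop-outs come from one sequence, leaving completers 2/10/10/10. Metformin is measured under three of the four treatments. With period in the model:

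| Treatments in the metformin model | Variance factor | Power at n = 32 |
|---|---|---|
| balanced 8/8/8/8 | 0.0625 | 0.904 |
| 2/10/10/10, three metformin treatments | 0.070 | 0.873 |
| 2/10/10/10, step 1 treatments only | 0.100 | 0.738 |

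So 0.904 is a balanced-sequence figure.

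**The case against.** The strongest reply is that nobody would be misled. The negation is obvious from the protocol and from the rest of the SAP sentence. SAP 5 bases the SAP on protocol section 9, and SAP 9 adopts the protocol's statistical methods, so the 9.9.3 PK set applies without being repeated. A subject withdrawn for vomiting is not a completer and never enters that set, so the immediate-release exception is not needed to reach that result. SAP 10.1 keeps a working pre-dose rule whatever SAP 12.2 says.

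Much of this stands:
- A reader might infer that the SAP plans to discard its evaluable subjects. The documents do not support that.
- A reader might infer that no PK set exists. Protocol 9.9.3 supplies one; only a cross-reference is missing.
- A reader might infer that the closed list forces all drop-outs into the analysis. It does not: its third case, as the protocol words it, already removes subjects lacking test or reference data. Only drop-outs holding both treatments of a comparison are left open, and reading 9.9.3 first and the list second settles them. Neither document states that order.

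What does not fall away is that the rules give wrong or empty results when followed as written. The completer argument does not help for diarrhoea, for which there is no withdrawal rule. It also depends on withdrawal happening, and protocol 7.3.4 opens by leaving withdrawal to the Principal Investigator's judgment.

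**Conclusion.** The point holds as a minor error of wording in operative rules: a reversed evaluability exclusion (twice in the SAP), a pre-dose rule with three different scopes, one of them void in this trial, and a vomiting exception that cannot apply to XR/MR tablets and does not agree with protocol 7.3.4.

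The planned 32 evaluable and 40 randomised subjects stand, with power 0.904 at CV 23% and ratio 0.95, assuming balanced sequences. It might be inferred that power stays between 0.904 (n = 32) and 0.953 (n = 40) however the set is read. That is not supported, since unequal losses across sequences can take it lower, as shown above.

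It might also be inferred that the reported intervals rest on the wrong subjects. SAP 12.1 reports no deviation and the analysed numbers are redacted, so the documents do not show that anyone was wrongly kept or removed.

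**What to change.** - **Evaluability:** restore 'do not' in SAP 10.1 and 12.2, so that the rule excludes subjects who do not provide evaluable data for both test and reference.
- **Pre-dose rule:** in both SAP sections, replace the present scope (including the food-effect wording) with that of protocol 9.9.4, so that it covers steps 1, 2 and 3.
- **Vomiting and diarrhoea:** reconcile protocol 7.3.4 item 9 with the exception in protocol 9.9.4 and SAP 10.1 and 12.2 as regards the analysis, including the release type and the 'or'/'and' difference. Which clinical rule applies is for the sponsor and investigator to settle.
- **Analysis set:** refer SAP 10.1 to the PK Analysis Set in protocol 9.9.3 and state that the removal list applies after that set is formed.

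The cost is a few sentences in two SAP sections and a short protocol clarification. The pre-specified primary set and the sample size do not change. Only if the reported intervals used a set other than that of 9.9.3 would they need to be re-run, or the departure declared.
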